4.2.1 Secondary efficacy variables

The main secondary efficacy variable is as follows:

- Proportion of responders to BRV treatment from Baseline to 3 hours after the initial BRV dose

A BRV responder is defined as a subject who achieves the following reduction in seizure burden (ENS in minutes per hour) without need for rescue medication, compared to the seizure burden measured during the Baseline Period immediately prior to BRV administration, evaluated for a 2-hour period starting 1 hour after the start of initial BRV treatment:

- At least 80% reduction in nonsevere seizure burden

(Nonsevere seizure burden is defined as $\leq 50\%$ seizure activity on VEEG in all 30-minute timespans)

OR

- At least 50% reduction in severe seizure burden

(Severe seizure burden is defined as $> 50\%$ seizure activity on VEEG in any 30-minute timespan). Timespans of 30 minutes refer to the following intervals within the 2-hour period: 0 to ≤ 30 minutes, > 30 to ≤ 60 minutes, > 60 to ≤ 90 minutes, and > 90 to ≤ 120 minutes.

For this study, an ENS is defined as an EEG seizure lasting for at least 10 seconds on VEEG. Baseline seizure burden is defined as seizure burden measured on the continuous VEEG (total ENS in minutes per hour) during a period of up to 1 hour immediately prior to the first administration of study drug.

In addition, the secondary efficacy variables will include:

- Proportion of subjects with at least 80% reduction in nonsevere seizure burden from Baseline to 3 hours after the initial BRV treatment
- Proportion of subjects with at least 50% reduction in severe seizure burden from Baseline to 3 hours after the initial BRV treatment
- Absolute reduction in average seizure burden measured by continuous VEEG from Baseline to the end of the 96-hour Evaluation Period
- Percent reduction in average seizure burden measured by continuous VEEG from Baseline to the end of the 96-hour Evaluation Period
- Proportion of BRV responders at the end of the 96-hour Evaluation Period
- Proportion of subjects who are seizure-free (100% reduction in seizure burden from Baseline) at 24 hours following the start of initial BRV treatment, categorized by subjects with nonsevere or severe seizure burden at Baseline

- Time to reduction in seizure burden for BRV responders (defined as the first timepoint when BRV responder criteria are met)
- Seizure freedom at the end of the Down-Titration Period

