3 DATA ANALYSIS CONSIDERATIONS

3.1 General presentation of summaries and analyses

Statistical analysis and generation of tables, figures, subject data listings, and statistical output will be carried out using SAS® Version 9.3 or higher.

Descriptive statistics, such as the number of subjects with available measurement (n), mean, standard deviation (SD), median, minimum value, and maximum value for quantitative variables, and counts and percentages for categorical variables, will be provided. Confidence intervals (95% CIs) will be provided for efficacy variables.

Unless otherwise noted, denominator for percentages will generally be based on the set of subjects with at least 1 assessment at the time point or at least 1 assessment during the time interval being summarized.

Decimal places for descriptive statistics will always apply the following rules:

- “n” will be an integer.
- Mean, SD and median will use 1 additional decimal place compared to the original data.
- Minimum and maximum will have the same number of decimal places as the original value.

Unless otherwise noted, all percentages will be displayed to 1 decimal place. No percentage will be displayed for zero counts, and no decimal will be presented when the percentage is 100%.

In general, descriptive summaries will be used to present study results overall (for the Confirmatory Cohorts) and by cohorts (Exploratory Cohort and each individual Confirmatory Cohort).

Subject data listings will be provided and will present source data and key derived variables for statistical analyses.

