4.8 Examination of subgroups

All efficacy variables will be analyzed by

1. Primary cause of seizure subgroups: HIE, ischemic stroke, intracranial hemorrhage, epileptic encephalopathy/genetic epilepsy, intracranial infection, brain malformation, inborn error of metabolism, undetermined causes, other.
2. Concomitant use of hypothermia subgroups: yes, no.

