8.2.4 Derivations of the secondary efficacy variables

The following secondary efficacy variables are defined as follows:

- Proportion of subjects with at least 80% reduction in non-severe seizure burden from Baseline to 3 hours after the initial BRV treatment [*derivations*: see the definition of baseline non-severe seizure burden in [Section 8.1.2.1](#); reduction of at least 80% in non-severe seizure burden from baseline is defined as a $\geq 80\%$ difference between average per hour seizure burden at baseline (calculated over the 1-hour Baseline Period) and average per hour seizure burden calculated over 3 hours after the start of initial BRV treatment divided by the average per hour seizure burden at baseline and multiplied by 100. The numerator is defined as the number of subjects with the 80% reduction described above. The denominator is defined as the number of subjects in the FAS from Confirmatory Cohorts with baseline non-severe seizure burden.]
- Proportion of subjects with at least 50% reduction in severe seizure burden from Baseline to 3 hours after the initial BRV treatment [*derivations*: see the definition of baseline severe seizure burden in [Section 8.1.2.2](#); reduction of at least 50% in severe seizure burden from baseline is defined as a $\geq 50\%$ difference between average per hour seizure burden at baseline (calculated over the 1-hour Baseline Period) and average per hour seizure burden calculated over 3 hours after the start of initial BRV treatment divided by the average per hour seizure burden at baseline and multiplied by 100. The numerator is defined as the number of subjects with the 50% reduction described above. The denominator is defined as the number of subjects in the FAS from Confirmatory Cohorts with baseline severe seizure burden.]

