- Proportion of subjects who are seizure-free (100% reduction in seizure burden from Baseline, i.e. those subjects whose seizure burden disappeared) at 24 hours following the start of initial BRV treatment, categorized by subjects with non-severe or severe seizure burden at Baseline [**derivations**: the numerator is the number of subjects with 100% reduction in seizure burden from Baseline or no ENS during the last 2 hours of the 24-hour time period following the start of initial BRV treatment, see the definition of baseline seizure burden in [Section 8.1](#), the denominator is defined as the number of subjects in the FAS from Confirmatory Cohorts.]
- Time to reduction in seizure burden for BRV responders (defined as the first time point when BRV responder criteria are met) [**derivations**: the time to reduction in seizure burden is measured in hours, defined as the first time point (date and time) when BRV responder criteria are met minus the date and time of the first BRV dose, event is defined as response to BRV, subjects will be evaluated for response at the following time points: 3 hours, 4 hours, 5 hours, etc., 96 hours after the initial BRV dose. Response will be calculated referring to the last 1 hour prior to the time point. Non-responder for the analysis of other than main efficacy variable subjects defined in the [Section 8.1](#) are censored with time to censoring defined as the date and time of the event defining the non-responder status (drop out due to lack of BRV efficacy, switch over to another AED treatment, used >1 dose of rescue medication following the first 3 hours after initiation of BRV treatment) or date and time of the end of the Evaluation Period in case there are no events of response or non-response minus the date and time of first BRV dose; when the time is not collected, use HH:MM=23:59.]
- Seizure freedom at the end of the Down-Titration Period (Confirmatory Cohorts only) [**derivations**: defined as proportion of subjects who are seizure-free at the end of the Down-Titration Period, the numerator is the number of subjects with seizure-freedom defined as no ENS at the end of the Down-Titration Period, i.e. no ENS during 1 hour of VEEG, the denominator is defined as the number of subjects in the FAS from Confirmatory cohorts with VEEG data at the end of the Down-Titration Period.]

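### Seizure freedom at 24 h is split by Baseline severity, but its stated denominator is the whole Confirmatory FAS; applied to stratum counts, that denominator understates the stratum rates.

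*SAP*

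**What the plan says.** SAP 8.2.4 describes the 24-hour seizure-freedom variable as "categorized by subjects with non-severe or severe seizure burden at Baseline". For the derivation, "the numerator is the number of subjects with 100% reduction in seizure burden from Baseline or no ENS during the last 2 hours" of the first 24 hours, and "the denominator is defined as the number of subjects in the FAS from Confirmatory Cohorts". Neither part mentions severity.

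Earlier in the same section, the two 3-hour variables that depend on Baseline severity are written differently. For the non-severe variable: "The denominator is defined as the number of subjects in the FAS from Confirmatory Cohorts with baseline non-severe seizure burden". For the severe variable: "The denominator is defined as the number of subjects in the FAS from Confirmatory Cohorts with baseline severe seizure burden".

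Other places that might have supplied a stratum denominator do not:

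- SAP 3.1 has a default: "Unless otherwise noted, denominator for percentages will generally be based on the set of subjects with at least 1 assessment at the time point". It yields to a specific definition, and it does not restrict by severity.
- SAP 4.8 lists cause of seizure and hypothermia ("Concomitant use of hypothermia subgroups: yes, no") as subgroups. Baseline severity is not among them.
- Protocol 4.2.1 has the same split ("categorized by subjects with nonsevere or severe seizure burden at Baseline") without a denominator, and Protocol 13.5.1 repeats it, also without one.

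**The concern.** A rate reported by severity category is normally read as the proportion within that category. The stated denominator does not deliver this if it is used with counts taken within each stratum. The percentages would then mix two things: how often babies in a stratum became seizure-free, and how large the stratum was.

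A secondary objective (SAP 2.1.2, Protocol 3.2) is efficacy in severe and non-severe seizure burden, so readers will set the two percentages side by side. SAP 8.2.5 also calls for 95% confidence intervals on categorical secondary variables, and these would be built on the wrong n.

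**Working it through.** The documents state no rate or precision for this variable, so there is no planned figure to reproduce. The check is arithmetic on the definition.

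**Inputs**

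- Denominator as written: the Confirmatory FAS, N. SAP 2.4 plans at least 36 Confirmatory subjects; N = 36 is assumed here.
- Strata: SAP 8.1.2.1 and 8.1.2.2 make severe and non-severe Baseline burden mutually exclusive. Call the stratum size n and its number of seizure-free subjects x.
- Severity split and true rates: not given in the documents. Assumed splits (non-severe/severe) run from 9/27 to 27/9, with a true rate of 33.3% or 50% in both strata.

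**Formula**

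Rate as written, applied to stratum counts: x/N = (n/N) × (x/n). This is the stratum rate multiplied by the stratum's share of the FAS. It follows that:

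- any non-zero stratum rate is understated whenever both strata contain subjects;
- the two reported rates add up to the overall rate;
- neither can exceed its stratum's share of the FAS.

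**Numbers: 24/12 split, 50% seizure-free in each stratum, exact (Clopper-Pearson) 95% CIs**

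| Stratum | Stated denominator | Stratum denominator |
|---|---|---|
| Non-severe | 12/36 = 33.3% (18.6 to 51.0) | 12/24 = 50.0% (29.1 to 70.9) |
| Severe | 6/36 = 16.7% (6.4 to 32.8) | 6/12 = 50.0% (21.1 to 78.9) |

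Two equal rates appear to differ two-fold, and the severe interval on the stated denominator does not contain the stratum rate of 50%.

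**Range over other assumptions**

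- 18/18 split, 50% in each: 9/36 = 25.0% in both strata, against 9/18 = 50.0%.
- True 33.3% in both strata: a stratum of 9 reports 3/36 = 8.3% and a stratum of 27 reports 9/36 = 25.0%, so reported rates run from 8.3% to 25.0% across the splits.
- 20/16 split with unequal rates (10 and 4 seizure-free): 10/36 = 27.8% and 4/36 = 11.1%, against 10/20 = 50.0% (27.2 to 72.8) and 4/16 = 25.0% (7.3 to 52.4).
- Every baby seizure-free, 24/12 split: 24/36 = 66.7% and 12/36 = 33.3%, against 100% in both.

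**The fully unsplit reading**

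If both parts are taken exactly as written, with no stratum restriction, the result is one overall proportion. SAP 8.2.4 already provides that figure: its seizure-free-by-time-interval variable includes 24 hours, looks at the preceding 2 hours of VEEG, and uses the full Confirmatory FAS. The severity split is therefore what this variable adds.

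**The case against.** The strongest reply is that the understatement needs an asymmetric reading: severity applied to the numerator but not to the denominator, when the SAP writes severity into neither. A programmer could take the split as applying to both and obtain correct stratum rates.

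The SAP's own habits lend this some support. SAP 8.2.1 gives the main secondary variable's denominator as the Confirmatory FAS, and SAP 8 and 8.2.2 then ask for results by cohort, cause of seizure and hypothermia without restating it. Nobody would divide a single cohort's responders by the whole Confirmatory FAS. The 3-hour severity variables can also be distinguished: they are two separate variables, each with its own threshold and each existing only within one stratum.

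This stands in part. A reader might infer that the SAP deliberately divides stratum counts by the full FAS, or that both stratum rates will certainly be understated. The documents support neither. They support a conditional statement: the rates are understated if the stated denominator is applied to stratum counts.

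The reply does not remove the point. Here the severity split is part of the variable's own definition, not a later subgroup display, and the unsplit reading only duplicates a figure given elsewhere. The same section shows how a stratum denominator is written when one is meant. A programmer who produces correct rates has to depart from the denominator on the page.

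A reader might also infer that severe and non-severe babies could not be compared at all. That goes too far. SAP 8.2.5 requires counts and a listing, and the 3-hour severity variables carry the stratum sizes as their denominators, so the stratum rates could be recovered.

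**Conclusion.** The point holds in conditional form. SAP 8.2.4 pairs a severity-split variable with an unrestricted FAS denominator, and no other section corrects it. Applied to stratum counts, that denominator scales each rate by the stratum's share of the FAS. With 36 subjects and a true 50% in both strata, the reported rates would be 33.3% and 16.7% for a 24/12 split, or 25.0% in each for 18/18.

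The size depends wholly on the severity mix and the seizure-free rates, which are assumptions here. The direction does not, provided both strata contain subjects and the stratum has at least one seizure-free subject.

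The consequence is limited. SAP 4.5 makes all analyses descriptive with no statistical tests, and this is not the main secondary variable. What is at risk is the accuracy of the two reported stratum rates and their confidence intervals. It is worth correcting before the tables are programmed.

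**What to change.** In SAP 8.2.4, for seizure freedom at 24 hours, define both parts within the stratum: the numerator as seizure-free subjects, and the denominator as all subjects, among FAS subjects from the Confirmatory Cohorts with non-severe (respectively severe) Baseline seizure burden. This matches the 3-hour severity variables in the same section. An overall row on the full FAS is optional, because the time-interval variable already gives that rate at 24 hours.

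The cost is one phrase in the SAP. It needs no new data and no change to the protocol, which states no denominator for this variable.

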Rescue medication should be given if the following occurs:

- There is no improvement in seizure burden within the first 3 hours after administration of BRV.
- Seizure burden is unacceptable to the Investigator, in which case rescue medication can be given earlier at any time, but ideally not in the first 3 hours after the initial administration of BRV.

Subjects in the Confirmatory Cohorts are allowed to switch over from BRV to another AED (eg, MDZ or PHT), if needed. Subjects discontinuing BRV treatment during the Evaluation Period should start the Down-Titration Period while completing the Evaluation Period in parallel for the full 96 hours. In this case, subjects will complete all study assessments, except the collection of blood microsamples for the determination of BRV plasma concentrations. Ideally, changing or adding a new treatment should not occur during the first 3 hours after the initial administration of BRV. Subjects who are switched from BRV to another AED will not be eligible to participate either in the BRV Extension Period or the long-term study.

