7.8.3 Rescue medication

Any treatment initiation with a new AED, or any increase of dose or frequency of an existing concomitant AED for the treatment of seizures during the Evaluation Period is considered rescue treatment. Rescue medication can be given at any time if considered necessary by the Investigator.

However, during the Evaluation Period rescue medication should not be administered – if possible – in the following time frames:

- During the first 3 hours after the initial dose of BRV for the Confirmatory Cohorts. If this occurs, subjects will be considered BRV nonresponders for the evaluation of the main efficacy variable.

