4.2.3 Handling of dropouts or missing efficacy data

For subjects who drop out during the Evaluation Period, the number of hours from the start of the Evaluation Period to the time of withdrawal (in hours) will be considered for analysis. Subjects in the Confirmatory Cohorts who are withdrawn or are switched over to another AED treatment prior to the Evaluation Period or are administered >1 dose of rescue medication (including BZDs) following the first 3 hours after initial BRV treatment started will be considered BRV non-responders.

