- Absolute reduction in average seizure burden measured by continuous VEEG from Baseline to the end of the 96-hour Evaluation Period [*derivations*: see the definition of baseline seizure burden and of average per hour seizure burden in [Section 8.1](#), average per hour over 96-hour Evaluation Period seizure burden is calculated as the total seizure burden during the 96-hour Evaluation Period divided by 96, the number of hours in the Evaluation Period, average per hour seizure baseline seizure burden is calculated as the total seizure burden over 1-hour Baseline Period divided by 1. The **absolute reduction** in average per hour seizure burden is defined as the average per hour seizure burden at the end of the 96-hour Evaluation Period minus average per hour baseline seizure burden]

- Percentage reduction in average seizure burden measured by continuous VEEG from Baseline to the end of the 96-hour Evaluation Period [**derivations**: see the definition of baseline seizure burden and of average per hour seizure burden in [Section 8.1](#), average per hour over 96-hour Evaluation Period seizure burden is calculated as the total seizure burden during the 96-hour Evaluation Period divided by 96, the number of hours in the Evaluation Period, average per hour seizure baseline seizure burden is calculated as the total seizure burden over 1-hour Baseline Period divided by 1. The **percentage reduction** is defined as the absolute reduction in average per hour seizure burden divided by the average per hour baseline seizure burden and multiplied by 100.]
- Proportion of BRV responders during the 96-hour Evaluation Period (measured at the end of the 96-hour Evaluation Period) [**derivations**: see the definition of BRV responders for other than main efficacy variable in [Section 8.1](#), the post-baseline seizure burden will be evaluated during the last 1 hour of the 96-hour Evaluation Period, the denominator is defined as the number of subjects in the FAS from Confirmatory Cohorts.]

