8.2.5 Analysis of the secondary efficacy variables

Categorical secondary efficacy variables will be summarized using descriptive statistics (counts and proportions with the 95% CIs). Continuous key efficacy variables will be analyzed descriptively as described in [Section 3.1](#).

Time to reduction in seizure burden will be summarized descriptively by individual Confirmatory Cohorts and for all combined Confirmatory Cohorts, the cumulative number of events (response to BRV), Kaplan-Meier estimates at each hour during the Evaluation Period and median time to seizure burden reduction with 95% confidence interval will be provided. Also, graphical displays of Kaplan-Meier curves will be provided for each cohort separately.

A listing of secondary efficacy variables will be provided for the FAS.

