8.3 Statistical analysis of other efficacy variables

8.3.1 Derivations of other efficacy variables

The other efficacy variables are defined as follows:

- Absolute and percentage reduction from Baseline in seizure burden at evaluation periods of 0 hours to 3 hours, >3 hours to 6 hours, >6 hours to 12 hours, >12 hours to 24 hours, >24 hours to 36 hours, >36 hours to 48 hours, >48 hours to 72 hours, and >72 hours to 96 hours after the start of initial BRV treatment [*derivations*: see the definition of baseline seizure burden and of average per hour seizure burden in [Section 8.1](#), the **absolute reduction** is defined as the difference between the baseline average per hour seizure burden and average per hour seizure burden at evaluation periods of 0 hours to 3 hours, >3 hours to 6 hours, >6 hours to 12 hours, >12 hours to 24 hours, >24 hours to 36 hours, >36 hours to 48 hours, >48 hours to 72 hours, and >72 hours to 96 hours after the start of initial BRV treatment. The **percentage reduction** is defined as the absolute reduction in seizure burden divided by the baseline average per hour seizure burden and multiplied by 100.]
- Categorized percentage reduction from Baseline to the end of the 96-hour Evaluation Period in seizure burden (<-25% [worsening], -25% to <25% [no change], 25% to ≤50%, 50% to <80%, and ≥80%) [*Derivations*: The **percentage reduction** of seizure burden is defined as the difference between the average per hour baseline seizure burden and the average per hour seizure burden at the end of the 96-hour Evaluation Period divided by the average per hour baseline seizure burden and multiplied by 100. For the definition of the average per hour seizure burden, please see [Section 8.1](#).]
- Proportion of BRV responders by time interval at evaluation periods of 0 hours to 3 hours, >3 hours to 6 hours, >6 hours to 12 hours, >12 hours to 24 hours, >24 hours to 36 hours, >36 hours to 48 hours, >48 hours to 72 hours, and >72 hours to 96 hours after the start of initial BRV treatment [*derivations*: see the definition of BRV responders in [Section 8.1](#), for the numerator calculate the number of responders during the given above evaluation periods 0-3 hours, >3-6 hours, >6-12 hours, >12-24 hours, >24-36 hours, etc., the denominator is defined as the number of subjects in the FAS from Confirmatory Cohorts.]

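### Time to seizure-burden reduction censors BRV failures at the moment they fail, so the Kaplan-Meier curve overstates the proportion of FAS subjects responding once a failure precedes a response; the median may be affected too

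*SAP*

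**What the plan says.** SAP 8.2.4 checks response hourly from 3 h to 96 h after the first dose. Subjects classed as non-responders for variables other than the main one "are censored with time to censoring defined as the date and time of the event defining the non-responder status". The events listed are "drop out due to lack of BRV efficacy, switch over to another AED treatment, used >1 dose of rescue medication", the rescue doses being counted after the first 3 hours. Subjects with neither response nor failure are censored at the end of the Evaluation Period.

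SAP 8.2.5 reports "the cumulative number of events (response to BRV), Kaplan-Meier estimates at each hour during the Evaluation Period and median time to seizure burden reduction", with a 95% CI for the median and KM curves for each cohort. It plans no competing-risk estimate and no sensitivity analysis for this variable.

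Elsewhere the plan keeps such subjects in view. SAP 4.2.3 classes subjects with more than one rescue dose after 3 h as BRV non-responders. The responder proportion at 96 h, for which "the post-baseline seizure burden will be evaluated during the last 1 hour of the 96-hour Evaluation Period", has all FAS subjects in the Confirmatory Cohorts as its denominator. SAP 2.3.2 asks subjects who stop BRV to complete the full 96-hour Evaluation Period.

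**The concern.** KM censoring assumes that a censored subject has the same later chance of the event as those still at risk. Here subjects are censored because BRV failed them: they dropped out for lack of efficacy, moved to another AED, or needed repeated rescue. Failure of this kind is a competing outcome, and for subjects who stop BRV the SAP does not treat it as loss to follow-up. Removing these subjects from the risk set credits them with the later response rate of those still on BRV.

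The condition for bias is plausible. Protocol 5.1.2 calls for rescue when seizure burden has not improved within the first 3 hours, so failures can fall soon after 3 h and before later responses. Failure before the first response check is discouraged but not excluded: "Ideally, changing or adding a new treatment should not occur during the first 3 hours after the initial administration of BRV". Protocol 7.8.3 adds that "Rescue medication can be given at any time if considered necessary by the Investigator".

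At stake are the published curve, its hourly estimates and possibly the median, all of which can err only in favour of BRV.

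**Working it through.** **Inputs.** At least 36 Confirmatory subjects in three cohorts of 12 (SAP 2.4); hourly checks from 3 h and the censoring rule (SAP 8.2.4); KM with a median (SAP 8.2.5). The documents give no response or failure rates or times and no expected median. There is therefore no planned figure to reproduce, and every rate below is assumed.

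**Direction.** Let N be all subjects, R(t) the responders up to t, r the responders at a given check, n the number then at risk, and F the failures already removed. With no other early censoring, n + F = N − (earlier responders).

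- As planned: 1 − KM(t) = 1 − product of (1 − r/n).
- Failure as a competing event: the product of (1 − r/(n + F)) telescopes to 1 − R(t)/N, so cumulative incidence is R(t)/N.

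Since n ≤ n + F, each planned factor is no larger than its counterpart, and it is strictly smaller at any response check after a failure. So 1 − KM is never below R(t)/N and exceeds it from the first response that follows a failure. In 20,000 random data sets of 12 or 36 subjects there was no exception. The KM median was never later than the cumulative-incidence median.

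**Hand examples, N = 36.**

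1. Nine respond at 3 h, 12 fail at 3.5 h, then two respond at each of 4, 6 and 12 h. 1 − KM = 1 − (27/36)(9/15) = 55.0%, against 15/36 = 41.7%. KM reports a median of 12 h although fewer than half respond.
2. Nine respond at 3 h, six at 4 h, then 12 fail at 5 h. Both estimates are 15/36 = 41.7%: no bias.
3. Ten respond at 3 h, eight at 4 h, eight fail at 5 h, two respond at 10 h. 1 − KM = 1 − (18/36)(8/10) = 60.0%, against 20/36 = 55.6%. Both curves stand at exactly 50% from 4 h to 10 h, so the median is 4 h if exactly 50% counts and 10 h if it does not. Under either convention it is the same for both curves.
4. Thirteen respond, all at 3 h, after f failures before 3 h. 1 − KM = 13/(36 − f): 36.1%, 37.1%, 38.2%, 40.6%, 46.4% for f = 0, 1, 2, 4, 8.

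One cohort of 12: three respond at 3 h, three fail, two respond later. 1 − KM = 1 − (9/12)(4/6) = 50.0%, against 5/12 = 41.7%.

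**Simulation.** N = 36, 13 responders (13/36 = 36.1%), failures after 3 h, all others followed to 96 h, 4,000 runs per scenario. Mean 1 − KM at 96 h:

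| Assumed timing | 4 failures | 8 failures | 16 failures |
|---|---|---|---|
| Responses 3-24 h, failures 3-96 h | 36.6% | 37.2% | 38.5% |
| 10 of 13 responses at 3 h, rest 4-48 h; failures 3-24 h | 37.3% | 39.0% | 46.1% |
| Both 3-24 h | 38.7% | 41.9% | 52.3% |
| Responses 3-48 h, failures 3-24 h (early failures) | 39.8% | 44.7% | 61.0% |
| Ceiling, 13/(36 − failures) | 40.6% | 46.4% | 65.0% |

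**Median.** With 13 responders and 4 to 8 failures after 3 h, no run reports one. With 16 responders (16/36 = 44.4%) and 8 failures both spread over 3-24 h, KM reports a median in about 87% of runs although fewer than half respond. If 12 of the 16 respond at 3 h, the KM survivor function cannot fall below (24/36)(12/16) = 0.500. A median then appears in 0% of runs if the function must fall below 0.5, and in about 13% to 15% if exactly 0.5 counts.

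**The case against.** - **The target is not stated.** The variable's title refers to BRV responders, and KM censored at failure can be read as the response expected had failure not occurred. The SAP states no such hypothetical target, however, and independent censoring is hard to defend for lack-of-efficacy events. The derivation itself brings non-responders in, so a responders-only reading does not fit it. It stands that the FAS proportion is an assumed target, though the one that matches how the SAP treats these subjects elsewhere.
- **The right numbers are nearly there.** Cumulative event counts are planned, and dividing them by the FAS size gives the cumulative incidence if nobody is censored early for another reason. The FAS-based interval proportions, where "for the numerator calculate the number of responders during the given above evaluation periods 0-3 hours" and the later intervals, are not inflated by this rule either. That lowers the harm but leaves a curve and median that may disagree with them.
- **The size may be small.** This stands. With 4 to 8 failures the mean excess is about 0.5 to 9 percentage points, while the 95% Wilson interval for 13/36 runs from 22% to 52%.
- **Who is censored is unsettled.** This also stands. SAP 8.2.4 points to a definition in Section 8.1, but 8.1.1 gives an explicit rescue and switch rule only for the first 3 hours. Protocol 13.5.1 bars any rescue after 3 h for responders. Protocol 10.1, for this variable by name, classes subjects with rescue or a switch after 3 h as responders. The bias arises under any definition that censors failures, whether by more than one dose or by any rescue. A reader might infer that it arises however the conflict is resolved. It does not: under a literal reading of Protocol 10.1 those subjects would not be censored as failures.

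**Conclusion.** The concern holds, with limited weight; the SAP should be changed. For the proportion of all FAS subjects who have responded to BRV by time t, the planned curve is too high from the first response that follows a failure, and equal before then. Under the assumed 36.1% response it would read about 37% to 45% at 96 h with 4 to 8 failures after 3 h, and about 61% with 16 early failures.

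Three stronger readings are tempting but unsupported. The median is not always too early: it may be unchanged, or not reached under either method. A large bias cannot be predicted, because the documents give no rates and there is none if every failure follows the last response. The trial's main efficacy result is not inflated by this rule: the 3-hour responder rate, the historical comparison and the event counts do not use the censored curve, and SAP 4.5 makes all analyses descriptive with no tests.

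**What to change.** **SAP 8.2.4.** State the target as the proportion of FAS subjects who have responded to BRV by time t, and treat the failure events as a competing event. Add ordinary censoring for loss of VEEG and for withdrawal unrelated to efficacy, and keep censoring at 96 h. The first two are new rules: 8.2.4 names only the failure events and the end of the Evaluation Period, and SAP 4.2.3 says only that "the number of hours from the start of the Evaluation Period to the time of withdrawal (in hours) will be considered for analysis".

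**SAP 8.2.5.** Report the Aalen-Johansen cumulative incidence of response at each hour with 95% CI, for each cohort and combined. Give a median only if the incidence reaches 50%, and state the convention for exactly 50%.

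**Separately,** reconcile Protocol 10.1 and 13.5.1 with SAP 4.2.3, 8.1.1 and 8.2.4, so that non-response after 3 h is defined once for analysis.

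The cost is SAP wording and a standard procedure option, with no new data. The downside for the sponsor is that the reported curve and median may be less favourable.
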